1. INTRODUCTION

1.1. Study Objectives

Primary Study Objectives	
• To assess the safety and tolerability of RVT-1401 in anti-acetylcholine receptor (AChR) antibody-positive myasthenia gravis (MG) patients over a 6-week treatment period• To examine the effects of RVT-1401 on total immunoglobulin G (IgG), IgG subclasses (1-4) and anti-AChR-IgG levels
Secondary Study Objectives	
• To examine RVT-1401 pharmacokinetics (PK) following repeat doses in patients with MG• To measure anti-RVT-1401 antibodies following repeat doses in patients with MG and assess any potential impact on PK or pharmacodynamics (PD)• To examine the effects of RVT-1401 on the Quantitative Myasthenia Gravis (QMG) score• To examine the effects of RVT-1401 on the proportion of patients with improvement on the QMG score by ≥ 3 points from baseline• To examine the effects of RVT-1401 on Myasthenia Gravis-Activities of Daily Living (MG-ADL) score• To examine the effects of RVT-1401 on the proportion of participants with an improvement on the MG-ADL score by ≥ 2 points• To examine the effects of RVT-1401 on the Myasthenia Gravis Composite (MGC) score• To examine the effects of RVT-1401 on the proportion of participants with an improvement on the MGC score by ≥ 3• To examine the effects of RVT-1401 on the Myasthenia Gravis Quality of Life (MG-QOL15r) score

Exploratory Study Objectives	[REDACTED]
Open-Label Extension Objective	
• To evaluate the effect of switching to an every 2-week dosing regimen of 340 mg RVT-1401 on all study endpoints

1.2. Study Design

Design Configuration and Subject Population	This is a Phase 2a, randomized, double-blind, placebo-controlled study with an open-label extension (OLE) to investigate the safety, tolerability, PK, PD, and efficacy of 2 dosing regimens of RVT-1401 in AChR antibody-positive MG patients.
Treatment Groups	
• RVT-1401 680 mg/week• RVT-1401 340 mg/week• Placebo
Key Eligibility Criteria	
• Myasthenia Gravis Foundation of America (MGFA) Class II-IVa and likely not in need of a respirator for the duration of the study as judged by the Investigator• Positive serologic test for anti-AChR antibodies at the screening visit and at least 1 of the following:
a. History of abnormal neuromuscular transmission test demonstrated by single-fiber-electromyography or repetitive nerve stimulation ORb. History of positive edrophonium chloride test ORc. Participant has demonstrated improvement in MG signs on oral cholinesterase inhibitors as assessed by the treating physician.• QMG score ≥ 12 at Screening and Baseline• Stable dose of MG treatment prior to randomization. For participants receiving azathioprine, other non-

	
steroidal immunosuppressive agents, steroids, and/or cholinesterase inhibitors as concomitant medications the following conditions will apply:
 
Azathioprine: treatment initiated at least 12 months ago and no dose changes in the last 6 months before ScreeningOther immunosuppressive treatment (e.g., methotrexate, cyclosporine, mycophenolate mofetil, and cyclophosphamide) initiated at least 6 months ago and no dose changes in the last 3 months before ScreeningStable dose of steroid treatment at least 6 weeks before BaselineCholinesterase inhibitors: stable dose for >1 week before Screening. Note: cholinesterase inhibitors must be held for at least 12 hours consistent with the revised manual for the QMG test as recommended by the MGFA, before the QMG and MGC assessments
Study Periods/Phases	
3-week screening period6-week treatment period12-week follow-up period or 6-week OLE period and a 6-week follow-up period

Figure 1. Study Design for Subjects Who do not Participate in the Open-Label Extension

[figure not shown]
[figure not shown]

Figure 2. Study Design for Subjects Who Participate in the Open-Label Extension

Schedule of Assessments

Time Window (days)		+1	+1	+/-1 day	+/-1 day	+/-1 day	+/-1 day	+/-1 day	+1	+/-2 days	+/-2 days	+/-2 days	+/-2 days	+/-2 days	+/-2 days
(MG-QOL15r) Score ^{6,7}															
Participant Satisfaction Questionnaire															X
Adverse events	X	X	X	X	X	X	X	X	X	X	X	X	X	X	X
Concomitant medication	X	X	X	X	X	X	X	X	X	X	X	X	X	X	X

1. Screening can take place over multiple days to ensure participants withhold cholinesterase inhibitors for at least 12 hours prior to the QMG and MGC assessments.

2. Vitals, ECG and blood draws for safety, PK, and PD assessment will be collected pre-dose on dosing days where specified.
3. Pregnancy tests will be collected pre-dose (via urine dipstick) on dosing days where specified. Serum pregnancy tests should be collected at screening, week 18, and early withdrawal.
4. Participants positive for anti-RVT-1401 antibody at Week 18 will be requested to return at approximately 6, 9, and 12 months post-dose for additional samples or until their result is no longer positive. However, for purposes of safety follow-up and database lock, participation ends at the Week 18 visit.
5. Local injection site reactions will be assessed at approximately 10 minutes post dose.
6. MG assessments will be assessed pre-dose when collected on dosing days
7. Subjects should be instructed to withhold cholinesterase inhibitors for at least 12 hours prior to the QMG and MGC assessments.

Schedule of Assessments: Open-Label Extension and 6-Week Follow-Up

	Screening		Treatment Period Week 1 (Days)		Treatment Period Week 6 (Days)		OLE and Follow-up Period Weekly Visit (Weeks)		Early Withdrawal Visit					
	1	2	3	4	5	6 (Day 36)	7	8	9	10	12	14	16	18
Study Timepoint (Weeks)	Within 21 Days	Day 1 (Baseline)	Day 3	Day 5	Day 8	Day 15 (Day 22)	Day 29	Day 36	Day 38	Day 40	7	8	9	
Time Window (days)			+1 day	+1 day	+1 day	+1 day	+1 day	+1 day	+1 day	+1 day	+/-2 days	+/-2 days	+/-2 days	+/-2 days
Informed consent	X ²													
Inclusion/exclusion criteria	X	X												
Demographics and medical history	X													
Height	X													
Body weight	X	X												
Complete physical examination	X	X												
Brief physical examination														
Vital signs ⁴	X	X	X	X	X	X	X	X	X	X	X	X	X	X
12-Lead electrocardiogram ³	X	X												
Pregnancy test ^{4,5} (females)	X	X												
QuantIFERON®-TB Gold	X													
Viral Serology	X													
Urinalysis ⁴	X	X												
Blood chemistry and hematology ⁴	X	X												
Serum complement (CH50, C3) ⁴	X													
Immunoglobulins (IgM, IgA) ⁴	X													
RVT-1401 PK sampling ⁴	X	X	X	X	X	X	X	X	X	X	X	X	X	X
Total IgG ⁴	X	X	X	X	X	X	X	X	X	X	X	X	X	X

	Screening ₁	Treatment Period Week 1 (Days)		Treatment Period Weekly Visit (Weeks)		Treatment Period Week 6 (Days)		OLE and Follow-up Period (Weekly Visit Weeks)						Early Withdrawal Visit			
		Within 21 Days	Day 1 (Baseline)	2 (Day 5)	3 (Day 8)	4 (Day 15)	5 (Day 22)	6 (Day 29)	Day 40	7	8	9	10	12	14	16	18
Study Timepoint (Weeks)	Within 21 Days																
Time Window (days)				+1 day	+1 day	+/-1 day	+/-1 day	+/-1 day	+/-1 day	+1 day	+1 day	+/-2 days	+/-2 days	+/-2 days	+/-2 days	+/-2 days	
Immunoglobins (IgG subclasses) ³		X	X	X	X	X	X	X	X	X	X	X	X	X	X	X	X
Anti-RVT-1401 antibody ^{4,6}		X															X
Nab Assessment ⁴	X																X
anti-AChR antibody ³	X	X	X	X	X	X	X	X	X	X	X	X	X	X	X	X	X
Drug administration	X																
Injection site reactions ⁷	X																
MG-ADL ^{3,9}	X																X
Quantitative Myasthenia Gravis (QMG) Score ^{8,9}	X	X															X
Myasthenia Gravis Composite (MGC) Score ^{7,8}	X																X
Myasthenia Gravis Quality of Life (MG-QOL15r) Score ^{8,9}	X																X
Participant Satisfaction Questionnaire																	X

	Screening ₁	Treatment Period Week 1 (Days)		Treatment Period Weekly Visit (Weeks)		Treatment Period Week 6 (Days)		OLE and Follow-up Period Weekly Visit (Weeks)						Early Withdrawal Visit					
		Day 1 (Baseline)	Day 3	Day 5	Day 8	Day 15	Day 22	Day 29	Day 36	Day 38	Day 40	7	8	9	10	12	14	16	18
Study Timepoint (Weeks)	Within 21 Days																		
Time Window (days)						+1 day	+1 day	+/-1 day	+/-1 day	+/-1 day	+/-1 day	+1 day	+1 day	+/-2 days	+/-2 days	+/-2 days	+/-2 days	+/-2 days	+/-2 days
Adverse events	X	X	X	X	X	X	X	X	X	X	X	X	X	X	X	X	X	X	X
Concomitant medication	X	X	X	X	X	X	X	X	X	X	X	X	X	X	X	X	X	X	X

1. Screening can take place over multiple days to ensure participants withhold cholinesterase inhibitors for at least 12 hours prior to the QMG and MGC assessments.

2. Consent for enrolment into the OLE needs to occur prior to Week 8.
3. Participants who complete the 6-week, randomized, double-blind treatment phase are eligible to participate in the OLE.
4. Vitals, ECG and blood draws for safety, PK, and PD assessment will be collected pre-dose on dosing days where specified.
5. Pregnancy tests will be collected pre-dose (via urine dipstick) on dosing days where specified. Serum pregnancy tests should be collected at screening, week 18, and early withdrawal.
6. Participants positive for anti-RVT-1401 antibody at Week 18 will be requested to return at approximately 6, 9, and 12 months post-dose for additional samples or until their result is no longer positive. However, for purposes of safety follow-up and database lock participation ends at the Week 18 visit.
7. Local injection site reactions will be assessed at approximately 10 minutes post-dose.
8. MG assessments will be assessed pre-dose when collected on dosing days.
9. Subjects should be instructed to withhold cholinesterase inhibitors for at least 12 hours prior to the QMG and MGC assessments.

1.3. Sample Size and Power

Planned Sample Size and Power Statement	
A sufficient number of participants will be enrolled to achieve approximately 21 evaluable participants. The sample size for this study was not determined using statistical methods. The sample size was chosen based on clinical and recruitment considerations.
 
However, the sample size of 14 active and 7 placebo participants will allow the study to show a 33% difference between either active arm and the placebo arm, assuming 90% power, equal standard deviations of 20 and an alpha of 0.05 using a 2-sided z-test for the primary endpoint of percentage change from baseline in IgG at Week 7.

--	--

3. TYPE OF PLANNED ANALYSIS AND ALPHA ALLOCATION

Per protocol, an interim analysis will occur after the last subject completes the Week 7 visit of the study. All efficacy endpoints will be evaluated for this analysis. It is noted that the planned interim/primary analysis is the final analysis of the complete dataset from the double-blind treatment period. The database is interim due to the follow-up period, in which safety data will continue to accrue and be updated.

Due to COVID-19 impact on the study, an interim analysis may be done after 15 subjects have completed Week 7, although the study is continuing. An interim analysis plan (IAP) will guide any interim analysis that is done. The IAP will document disclosure and safeguards to protect the integrity of the ongoing study.

A final analysis will occur when the last subject completes or discontinues the study and the database is locked.

An additional analysis of the anti-RVT-1401 antibody data will be performed if any subjects require follow-up testing. This analysis will focus solely on the antibody data and does not require any alpha correction. The CSR will be amended with this additional analysis if it is necessary.

Alpha is controlled through the conditional sequencing of hypotheses. No other adjustment for multiplicity is needed. The interim analysis, if done, will be executed for administrative purposes due to business needs in response to circumstances precipitated by COVID-19 issues. Alpha is allocated for the interim analysis of 0.0001, which is considered to be negligible; consequently, the final analysis has alpha = 0.05 preserved.

4. **BLINDING**

At the time of the finalization of this SAP, no unblinding of any kind has occurred. It is noted that the only unblinded personnel for the study are documented in planning documents. Immunovant supports strong process and has standard operating procedures (SOPs) consistent with written regulatory guidance and standard conventions to protect the blinding of this study.

Selected laboratory analytes that may reveal the treatment for individual subjects are conveyed and stored in protected spaces with controlled access to safeguard further the treatment given to specific subjects.

There are four sources of unblinding or potential unblinding for this study:

1. The randomization scheme, which was created by and is managed by contracted statisticians and personnel not otherwise involved in operational execution of the study and not involved with site activities.
2. The concentration values, which are conveyed and stored in controlled places, consistent with other companies.
3. The clinical trial material (CTM) to be assigned by computerized systems and dispensed by site personnel, which are managed by individuals not involved in operational execution of the study related to site activities,
4. Selected laboratory analytes, including IgG and albumin, which are known to be reduced with this compound, which are conveyed and stored in controlled-access space.

At the time of this SAP development, no one involved in the development of the SAP and no one involved in the query process is unblinded from any of these sources.

5. GENERAL CONSIDERATIONS FOR DATA ANALYSES

Data will be listed and summarized. Listings will be sorted by treatment, participant, day, and time and include both scheduled and unscheduled visits; table summaries will be presented by treatment include placebo, RVT-1401 340 mg, RVT-1401 680 mg, combined RVT-1401 group, and by scheduled visit.

Open label extension period will start from the date of the first OLE dose for each subject. Unless otherwise specified, data collected during OLE period will be included in the same listings, tables, and figures with data collected during double-blind period.

Unless stated otherwise, descriptive summaries for continuous variables will include n, mean, standard deviation (SD), median, first and third quartiles (Q1, Q3), minimum, and maximum. The geometric mean with associated 95% confidence interval (CI) and the between-participant coefficient of variation (CV) (%CVb) for PK parameters only will also be included. For categorical variables, n and percent will be used as summary statistics. Baseline is the last available assessment prior to time of the first dose unless it is specified otherwise. If there are multiple assessments collected on the same scheduled time, the average of these assessments will be used. For tabulated safety summaries, only the scheduled assessments will be included in the summary tables.

In general, summary statistics for raw variables will be displayed as follows: minima and maxima will be displayed to the same number of decimal places as the raw data. Means, medians, and quartiles will be presented to 1 more decimal place than the raw data ; standard deviations will be presented to 2 more decimal places than the raw data.

The numbers of decimal places for summary statistics of derived variables (i.e., variables that are not measured by the study site but are calculated for analysis based on other measured variables) will be determined on a case by case basis.

5.1. Analysis Populations

In accordance with guidance from the International Conference on Harmonisation of Technical Requirements for Registration of Pharmaceuticals for Human Use (ICH) *Statistical Principles for Clinical Trials E9* (1998), the following analysis populations will be used for all statistical analyses:

- The full analysis set (FAS) includes all randomized subjects who receive at least one dose of randomized study medication with at least one valid post-treatment value. The FAS is used for all efficacy analyses.
- The per-protocol set (PPS) includes all FAS subjects who do not have significant protocol violations, where a significant protocol violation is one that has the potential to affect analysis conclusions. Final determinations of significant protocol violations will be made at the final blinded data review meeting in accordance with guidance from ICH E9 (Statistical Principles).
- The safety analysis set (SAF) includes all subjects who received at least one dose of study medication. The SAF is used for all safety analyses.

- The Pharmacokinetic (PK) analysis set includes all subjects who undergo PK sampling and have evaluable concentration-time data for analysis.
- The Pharmacodynamic (PD) analysis set includes all subjects who received at least 1 dose of study medication and have a baseline PD measurement and at least 1 post-baseline PD measurement.
- The Open-label Extension (OLE) analysis set includes all subjects who enroll in the OLE study phase and receive at least 1 dose of study medication in the OLE. The OLE subjects will be summarized by actual treatment in the double-blind treatment period for safety and PK analyses and by randomized treatment assigned in the double-blind treatment period for other analyses based on the OLE population.

Solely to understand the influence of dropouts on study conclusions, the FAS will be partitioned into completers and dropouts.

Efficacy analysis will be done as randomized. Safety analysis will be done as treated. In the event the administered dose level is not consistent throughout the double-blinded period, the as treated arm will be determined by the highest dose level received during the double-blinded treatment period.

A summary of the number and percent of subjects in each analysis set will be provided by treatment group and in total. Analysis based on a 12-week Follow-up analysis set may be provided depending on the number of subjects who choose not to enroll in the OLE study phase.

5.2. Baseline

Baseline is defined as the last non-missing value prior to the date (time) of first dose of study drug unless otherwise specified. If there are multiple assessments collected on the same scheduled date and time, the average of these values will be used.

For the OLE, baseline is defined as the last non-missing value prior to the date (time) of first dose of study drug in the OLE.

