### **Expected Treatment Effect**

[figure not shown]
The proposed dosing regimens are expected to provide a sustained total IgG reduction of approximately 75-80% and 65-70% for Regimen A and B respectively, following the fourth or fifth dose. It is expected that the nadir IgG reduction will occur by the 5th dose and be maintained following the sixth dose before rising back to baseline over the next 6 to 8 weeks. These assumptions are supported by preliminary PD results, shown in Figure 1, from the ongoing Phase 1 clinical study RVT-1401-1001 (Section 3.2.3). In healthy participants, 4 weekly SC injections of 680 mg of RVT-1401 produced an average total IgG percent reduction from baseline of 78%.

For participants that enter into the OLE, IgG levels will rise over the 2-week interval between week 6 and the start of OLE dosing at week 8. The IgG levels are expected to oscillate between decreasing and increasing over the next 3 doses, with trough IgG levels expected to rise by 15-25% above the nadir levels achieved during the treatment phase in the double-blind part of the study. Subjects who switch to 340 mg every 2 weeks from the placebo treatment are expected to achieve an IgG reduction of approximately 35-45% after the last OLE dose. Upon completion of OLE dosing, all subject IgG levels are expected to return to baseline over the next 6-8 weeks.

In study RVT-1401-1001, the inter-individual variability in IgG reduction and PK was larger in the 340 mg cohort vs. the 680 mg cohort; this difference can be explained by lower receptor occupancy in the 340 mg cohort throughout the dosing interval across all individuals. It is also noteworthy that, with both doses, the variability in exposure decreased with repeat dosing. This may indicate that full receptor occupancy is not lost within the dosing interval, and that with subsequent doses, more receptors are being occupied or remain occupied.

In the repeat dose 340 mg cohort, there were some individuals who did not achieve nadir IgG concentration until after the last dose, indicating they may have not reached steady state. In contrast, most subjects in the 680 mg cohort achieved nadir concentration prior to the last dose and maintained that response until after the last dose, indicating steady state response was achieved. Data from this study will be used to support dose selection in future studies.

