### **Open-Label Extension Objective:**

The objective of the OLE is to evaluate the effect of switching to a every 2-week dosing regimen of 340 mg RVT-1401 on all study endpoints.

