### **Open-Label Extension**

If the participant is eligible and consents to enroll into the OLE, starting at Week 8 an additional 3 doses of 340 mg RVT-1401 will be administered over a 6-week period (every 2 weeks) followed by a 6-week follow up period.

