Injection site reactions 			X			X	X	X	X				X		X	X					
MG-ADL 			X			X	X	X	X			X	X		X	X			X	X	
Quantitative Myasthenia Gravis (QMG) Score 	X	X			X	X	X	X				X	X		X	X			X	X	

	Screening 	Treatment Period Week 1 (Days)			Treatment Period Weekly Visit (Weeks)				Treatment Period Week 6 (Days)			OLE and Follow-up Period Weekly Visit (Weeks)							Early Withdrawal Visit	
		Day 1 (Baseline)	Day 3	Day 5	2 (Day 8)	3 (Day 15)	4 (Day 22)	5 (Day 29)	6 (Day 36)	Day 38	Day 40	7	8	9	10	12	14	16	18	
Study Timepoint (Weeks)	Within 21 Days																			
Time Window (days)			+1 day	+1 day	+/-1 day	+/-1 day	+/-1 day	+/-1 day	+/-1 day	+1 day	+1 day					+/-2 days	+/-2 days	+/-2 days	+/-2 days	+/-2 days
Myasthenia Gravis Composite (MGC) Score 		X			X	X	X	X				X	X			X	X			X
Myasthenia Gravis Quality of Life (MG- QOL15r) Score 		X						X								X	X			X
Satisfaction Questionnaire												X								X
Adverse events	X	X	X	X	X	X	X	X	X	X	X	X	X	X	X	X	X	X	X	
Concomitant medication	X	X	X	X	X	X	X	X	X	X	X	X	X	X	X	X	X	X	X	

1. Screening can take place over multiple days to ensure participants withhold cholinesterase inhibitors for at least 12 hours prior to the QMG and MGC assessments.
2. Consent for enrollment into the OLE must occur prior to Week 8.
3. Participants who complete the 6-week, randomized, double-blind treatment phase are eligible to participate in the OLE
4. Vitals, ECG and blood draws for safety, PK, and PD assessment will be collected pre-dose on dosing days where specified.
5. Pregnancy tests will be collected pre-dose (via urine dipstick) on dosing days where specified. Serum pregnancy tests should be collected at screening, week 18, and early withdrawal.
6. Participants positive for anti- RVT-1401 antibody at Week 18 will be requested to return at approximately 6, 9, and 12 months post-dose for additional samples or until their result is no longer positive. However, for purposes of safety follow-up and database lock participation ends at the Week 18 visit.
7. Local injection site reactions will be assessed at approximately 10 minutes post dose.
8. MG assessments will be assessed pre-dose when collected on dosing days.
9. Subjects should be instructed to withhold cholinesterase inhibitors for at least 12 hours prior to the QMG and MGC assessments.

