### **10.3.6. Other Analyses**

#### **10.3.1. OLE and Follow up Analyses**

Data listings and summaries will be provided separately for the OLE and 12-Week Follow up Populations. Descriptive Analyses will be presented by randomized treatment assignment from the double-blind treatment period and overall. Baseline will be specified in the Statistical Analysis Plan. If there are multiple assessments collected on the same scheduled time, the average of these assessments will be used. Only the scheduled assessments will be included in the summary tables. All OLE and follow up analyses will be based on the OLE and 12-Week Follow up Populations, respectively. Ad hoc statistical analyses such as two sample t-test or Chi-Square test, may be performed for the changes or shifts at weeks 8, 10, and 12 separately. The significance will be evaluated at a 0.05 two-sided level for informational purposes only.

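### For participants from the active arms, the SAP's OLE baseline falls part-way through washout, so change from it does not estimate the effect of switching to every-2-week dosing

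*SAP*

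**What the plan says.** The OLE objective in Protocol section 4 is to "evaluate the effect of switching to a every 2-week dosing regimen of 340 mg RVT-1401 on all study endpoints". The protocol's section on OLE and follow-up analyses leaves the OLE baseline to the SAP, and SAP 5.2 supplies it: "For the OLE, baseline is defined as the last non-missing value prior to the date (time) of first dose of study drug" in the OLE.

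The first OLE dose is at Week 8 (Protocol 5.1: "starting at Week 8 an additional 3 doses of 340 mg RVT-1401 will be administered over a 6-week period"). The OLE schedule in Protocol 8.2 adds: "Vitals, ECG and blood draws for safety, PK, and PD assessment will be collected pre-dose on dosing days where specified". A further footnote there puts MG assessments before dosing as well. So wherever an endpoint is scheduled at Week 8, its OLE baseline is the Week 8 pre-dose value.

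Protocol 3.2.2 states what it expects of the switch against a different reference. For participants continuing into the OLE, it has "trough IgG levels expected to rise by 15-25% above the nadir levels achieved during the treatment phase" of the double-blind part. OLE results are to be "presented by randomized treatment assignment from the double-blind treatment period and overall". Ad hoc tests "may be performed for the changes or shifts at weeks 8, 10, and 12 separately".

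**The concern.** The last weekly dose is at Week 6 and the first OLE dose at Week 8. Protocol 3.2.2 says IgG takes 6 to 8 weeks to return to baseline after weekly dosing. At Week 8, participants from the two active arms have therefore lost some of the weekly-dosing effect and kept some of it. Participants from the placebo arm are at their untreated level.

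One label, change from OLE baseline, then covers two quantities. In placebo switchers it is the onset of drug effect. In the active arms it compares the every-2-week regimen with an arbitrary point on the washout curve. The objective asks how every-2-week dosing compares with the weekly dosing it replaces, and no passage defines a change from the end of weekly dosing. At stake is whether the OLE change tables answer the OLE's own question for the two active arms, about two thirds of participants under 1:1:1 randomisation if OLE uptake is similar across arms.

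**Working it through.** **Inputs (Protocol 3.2.2 unless noted).** Reduction R on weekly dosing: 75-80% (680 mg), 65-70% (340 mg). Recovery time T: 6-8 weeks. OLE trough in the active arms: 15-25% above nadir. Placebo switchers: 35-45% reduction. The model behind these projections is not in the documents, so they cannot be reproduced and are taken as given. Week 8 IgG is not given; the text says only that IgG rises between Weeks 6 and 8.

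**Step 1: Week 8 level.** Set Day 1 IgG = 100. Assume linear recovery from Week 6, so the reduction left at Week 8 is R × (1 - 2/T).
- 680 mg: 75 × (1 - 2/6) = 50 to 80 × (1 - 2/8) = 60.
- 340 mg: 65 × (1 - 2/6) = 43.3 to 70 × (1 - 2/8) = 52.5.

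Check against Phase 1 (680 mg, 78% reduction, within 30% of baseline at 5 weeks, taken as exactly 30%): linear 78 - 2 × (48/5) = 58.8; exponential 78 × exp(-2 × ln(78/30)/5) = 53.2. Both lie within 50-60.

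**Step 2: OLE trough.** Nadir = 100 - R. The documents do not say whether 15-25% means points of Day 1 IgG or is relative to nadir.
- Points: 680 mg 35-50, 340 mg 45-60.
- Relative: 680 mg 20 × 1.15 = 23 to 25 × 1.25 = 31.25; 340 mg 30 × 1.15 = 34.5 to 35 × 1.25 = 43.75.

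**Step 3: change from OLE baseline** = 100 × (trough / Week 8 level - 1). Extremes for 680 mg, points: R = 80, T = 6 gives 35/46.67 - 1 = -25%; R = 75, T = 8 gives 50/43.75 - 1 = +14%.

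Sensitivity to the recovery curve: a one-week plateau then linear, R × (1 - 1/(T - 1)); and exponential with 90% recovery at T, R × exp(-2 ln 10 / T).

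| Curve | Arm | Reduction left at Week 8 | Change, points | Change, relative |
|---|---|---|---|---|
| Linear | 680 mg | 50-60% | -25 to +14% | -51 to -29% |
| Linear | 340 mg | 43-53% | -16 to +17% | -35 to -15% |
| Plateau | 680 mg | 60-69% | -3 to +43% | -36 to -12% |
| Plateau | 340 mg | 52-60% | +2 to +38% | -22 to -1% |
| Exponential | 680 mg | 35-45% | -44 to -14% | -63 to -46% |
| Exponential | 340 mg | 30-39% | -33 to -5% | -49 to -31% |

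**Step 4: the same troughs on other references.**
- Against the weekly-dosing nadir (taken as about the Week 7 level): points, 680 mg +60% (15/25) to +125% (25/20) and 340 mg +43% (15/35) to +83% (25/30); relative, +15 to +25%.
- Against Day 1: points, 680 mg -50 to -65% and 340 mg -40 to -55%; relative, -69 to -77% and -56 to -66%.

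The sign on each of these references is the same under either reading. A negative change from OLE baseline runs opposite to the expected rise over weekly dosing; a positive one runs opposite to the suppression that persists against Day 1.

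**Step 5: pooling.** Midpoints (R = 77.5 and 67.5, T = 7, +20 points) give -5% and +1%. With -40% for placebo switchers and equal groups, overall change from OLE baseline is (-5 + 1 - 40)/3 = about -15%. Against Day 1 it is (-57.5 - 47.5 - 40)/3 = about -48%.

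**The case against.** The strongest reply is that the information is not lost. SAP 5 puts OLE data, unless otherwise specified, in the same tables and figures as double-blind data, and SAP 12 summarises actual PD values at every scheduled visit. A reader can follow each arm through Weeks 7, 8, 10 and 12. The Week 8 reference is right for placebo switchers and natural for OLE safety. The protocol calls the OLE analyses descriptive and any significance informational only. All of this stands. But SAP 5.2 gives an explicit OLE rule, and nothing says which baseline the joint tables use after Week 8, so two programmers could fill the change columns differently.

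Several stronger readings are tempting, and the documents do not support them:
- *The change always has the wrong sign, or active-arm IgG will appear to double.* The sign depends on an unstated curve and an ambiguous percentage. A doubling (25 to 50) needs no recovery by Week 8, against Protocol 3.2.2; the largest value above is +43%.
- *Active and placebo switchers move in opposite directions.* The active-arm change can also be negative.
- *A maintained clinical response will be scored as non-response.* MG-ADL of 10 on Day 1 and 6 at Weeks 8 and 12 is zero change from OLE baseline, but no visible passage scores OLE responders that way. The endpoints in SAP 9.4.1 run to Week 7 or by Week 7, and SAP 9.4.2 does not invoke the OLE baseline.
- *The Week 8 test is empty for everyone.* Participants who decline the OLE have no OLE baseline. The change is zero by construction only in the OLE population, and only for endpoints measured pre-dose at Week 8.
- *Every OLE baseline is at Week 8.* As far as the damaged schedule can be read, chemistry and hematology are taken at Week 7 and not Week 8.

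**Conclusion.** The point holds for the two active arms and for endpoints measured pre-dose at Week 8. The reference is neither untreated nor on weekly dosing, and at Week 8 IgG is still about 50-60% (680 mg) or 43-53% (340 mg) below Day 1 under linear recovery. Across the other two curves the range is 35-69% and 30-60%. Change from that reference does not estimate the effect of the switch, and the protocol's own figures allow either sign. This rests on the protocol's projected reductions and recovery time, an assumed recovery shape, and both readings of the 15-25% figure. Nothing here touches the double-blind comparison or any primary conclusion. It is an inexpensive improvement to a descriptive analysis.

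**What to change.** Amend SAP 5.2 and the OLE table shells:
- For participants randomised to either active arm, report OLE PD and MG-score changes, and any OLE responder status, from the Day 1 baseline. Also report them from Week 7, the end of weekly dosing, where a Week 7 value is scheduled. Check the OLE schedule for IgG subclasses and MG-QOL15r, which appear to lack one.
- Keep the pre-OLE baseline for placebo switchers and for OLE safety changes.
- State which baseline the joint double-blind and OLE tables use after Week 8.
- Do not pool ex-placebo with ex-active participants for change from OLE baseline.
- In the OLE population, refer any ad hoc Week 8 test of endpoints measured pre-dose at Week 8 to Day 1 or Week 7.

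The cost is SAP wording and extra table columns; most of the values are already scheduled. The downside is two reference points in the OLE tables, which need clear labels.
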